7.4. Liver Function Monitoring and Study Drug Management

ALT, AST, alkaline phosphatase (ALP) and total, direct, and indirect bilirubin will be obtained in accordance with the schedule of events.

Patients with abnormal hepatic laboratory values [ie, ALP, AST, ALT, total bilirubin (TBL)] or signs/symptoms of hepatitis should be evaluated to determine if the criteria for permanent discontinuation of study drug have been met. Patients who meet the criteria for permanent discontinuation must not be re-challenged. If a PI decides to hold study drug for abnormal lab values that don't meet the mandated threshold, this is also considered a permanent discontinuation and the patient must not be re-challenged.

Criteria for permanent discontinuation of study drug due to potential hepatotoxicity

- Elevation of either AST or ALT according to the following schedule:

Baseline AST or ALT Value	AST or ALT Elevation
Any	>8 × ULN at any time
Any	>5 × ULN but <8 × ULN for ≥2 weeks
Any	>5 × ULN but <8 × ULN and unable to adhere to enhanced monitoring schedule
Any	>3 × ULN with clinical signs or symptoms that are consistent with hepatitis (such as right upper quadrant pain/tenderness, fever, nausea, vomiting, jaundice)

OR

- TBL $>3 \times$ ULN at any time

Study drug **must** be also discontinued permanently if ALL of the criteria below are met:

- TBL $>2 \times$ ULN or international normalized ratio (INR) >1.5

AND

- increased AST or ALT from the relevant baseline value as specified below:

Baseline AST or ALT Value	AST or ALT Elevation
$<ULN$	$>3 \times ULN$

AND

- no other cause for the combination of the above laboratory abnormalities is apparent. Important alternative causes for elevated AST/ALT and TBL values include, but are not limited to:

- hepatobiliary tract disease
- viral hepatitis (eg, Hepatitis A/B/C/D/E, Epstein-Barr Virus, cytomegalovirus, Herpes Simplex Virus, Varicella, toxoplasmosis, and Parvovirus)
- right sided heart failure, hypotension, or any cause of hypoxia to the liver causing ischemia
- exposure to hepatotoxic agents/drugs or hepatotoxins, including herbal and dietary supplements, plants and mushrooms
- heritable disorders causing impaired glucuronidation (eg, Gilbert’s Syndrome, Crigler-Najjar syndrome) and drugs that inhibit bilirubin glucuronidation (eg, indinavir, atazanavir)
- alpha-one antitrypsin deficiency
- alcoholic hepatitis
- autoimmune hepatitis
- Wilson’s disease and hemochromatosis
- nonalcoholic fatty liver disease including steatohepatitis
- nonhepatic causes (eg, rhabdomyolysis, hemolysis)

Patients who clearly meet the criteria for permanent discontinuation must never be re-challenged.

Additional Clinical Assessments and Observation

All patients in whom the study drug is permanently discontinued due to meeting the hepatic safety threshold as described above are to undergo a repeat test and a period of “close

observation” until abnormalities have stabilized and returned to normal (or returned to the patient’s baseline levels). Assessments that are to be performed during this period include:

- Retesting of AST, ALT, ALP, bilirubin (total and direct), and obtaining an INR within 48 hours
- In cases of TBL $>2 \times$ ULN or INR >1.5 , retesting of liver tests, bilirubin (total and direct), and INR within 48 hours

Confirmed abnormal liver function tests (LFTs) should be repeated 2-3 times weekly then weekly or less if abnormalities stabilize or the study drug has been discontinued and the patient is asymptomatic. Follow the patient and the laboratory tests (ALT, AST, TBL, INR) until all laboratory abnormalities return to baseline or normal.

- Initiate investigation of alternative causes for elevated AST or ALT and/or elevated TBL:
 - Obtain complete blood count (CBC) with differential to assess for eosinophilia
 - Obtain serum total immunoglobulin IgG, Anti-nuclear antibody (ANA), Anti Smooth Muscle Antibody, and Liver Kidney Microsomal antibody 1 (LKM1) to assess for autoimmune hepatitis
 - Obtain serum acetaminophen (paracetamol) levels
 - Obtain viral serologies
 - Obtain creatine phosphokinase, haptoglobin, lactate dehydrogenase, and peripheral blood smear
 - Perform appropriate liver imaging if clinically indicated
- Obtain a more detailed history of:
 - Prior and/or concurrent diseases or illness
 - Exposure to environmental and/or industrial chemical agents
 - Symptoms (if applicable) including right upper quadrant pain, hypersensitivity type reactions, fatigue, nausea, vomiting and fever
 - Prior and/or concurrent use of alcohol, recreational drugs and special diets
 - Concomitant use of medications (including non-prescription medicines and herbal and dietary supplements), plants, and mushrooms
- Obtain appropriate blood sampling for pharmacokinetics (PK) analysis if this has not already been collected
- Obtain hepatology consult (liver biopsy may be considered in consultation with an hepatologist)

Clinically significant elevated transaminases and/or bilirubin and manifestations of liver toxicity (eg, rash, abdominal pain, nausea and vomiting, fatigue, dark-colored urine, light-colored bowel movements, jaundice, loss of appetite, fever), including elevations that prompt study drug discontinuation, are considered adverse events of special interest and must be recorded on the appropriate CRF and reported to Cytokinetics Drug Safety within 24 hours of awareness.

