 110. Clinical laboratory findings within the normal range, or if outside the normal range, not deemed clinically significant by the Investigator, except as specifically indicated as laboratory exclusion in [Section 5.2](#).
 111. Able to swallow whole tablets at the time of screening
 112. Male patients, who have not had a vasectomy with medical assessment of surgical success, or a confirmed sperm count of zero, are eligible to participate if they agree to the following during the trial and for at least 10 weeks after the last dose of study drug:
 - a. Refrain from donating spermPlus when their female partner is of childbearing potential must either:
 - b. Be abstinent from heterosexual intercourse and agree to remain abstinentOR
Must agree to use a male condom AND have his female partner use a highly effective method of contraception during the study (as described in Appendix 3 [[Section 10.3](#)]), and also for at least 4 weeks after the last dose of study drug.
 113. A female patient is eligible to participate if she is not pregnant or breastfeeding, and at least one of the following conditions applies:
 - a. Is not a woman of childbearing potential (WOCBP; as described in Appendix 3 [[Section 10.3](#)])OR
Is a WOCBP and using a highly effective method of contraceptive during the study (as described in Appendix 3 [[Section 10.3](#)]) and also for at least 4 weeks after the last dose of study drug, and her male partner must agree to use a male condom during the trial and for at least 4 weeks after the last dose of study drug.
 - b. A WOCBP must have a negative pregnancy test (urine or serum as required by local regulations) within 3 days before the first dose of study drug.

Note: The investigator is responsible for review of medical history, menstrual history, and recent sexual activity to decrease the risk for inclusion of a woman with an early undetected pregnancy.

Contraceptive use by men or WOCBPs should be consistent with the guidance in Appendix 3 ([Section 10.3](#)) and local regulations regarding the methods of contraception for those participating in clinical studies.
114. Able to complete all screening procedures.
115. Must be either on the combination product (brand name only) of sodium phenylbutyrate and taurursodiol (also known as TUDCA, ursodoxicoltaurine or Tauroursodeoxycholic

acid) for ≥ 51 days prior to screening or not have taken it for at least 30 days prior to screening

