5.2. Exclusion Criteria

Patients will be excluded from the trial if any of the following criteria apply:

201. Other medically significant neurological conditions that could interfere with the assessment of ALS symptoms, signs or progression.
202. Presence at screening of any medically significant cardiac, pulmonary, gastrointestinal, musculoskeletal, or psychiatric illness that might interfere with the patient's ability to comply with study procedures or that might confound the interpretation of clinical safety or efficacy data, including, but not limited to:
 - a. Poorly controlled systemic hypertension
 - b. Clinically significant electrocardiogram (ECG) abnormalities that require medical attention (ie, persistent atrioventricular conduction block $>$ first degree, or acute myocardial ischemic changes)
 - c. New York Heart Association Class II or greater congestive heart failure
 - d. Chronic obstructive pulmonary disease
 - e. Gastrointestinal disorder that is likely to impair absorption of study drug from the gastrointestinal tract
 - f. $eGFR_{Cr}$ and $eGFR_{CysC} < 45.0$ mL/min/1.73 m² at screening
 - g. ALT or AST $\geq 3 \times$ ULN at screening
 - h. Urine protein creatinine ratio > 1 mg/mg (113 mg/mmol) at screening
 - i. Total bilirubin (TBL), direct or indirect bilirubin above the ULN.
 - j. History of Gilbert's Disease, Dubin-Johnson syndrome, or Rotor syndrome
 - k. Poorly controlled or brittle diabetes mellitus
 - l. Amputation of a limb
 - m. Cognitive impairment, related to ALS or otherwise that impairs the patient's ability to understand and/or comply with study procedures and provide informed consent
 - n. Cancer currently being treated (other than basal cell carcinoma, carcinoma in situ of the cervix, or squamous cell carcinoma of the skin excised with clean margins) or a history of cancer with an expected survival of less than 5 years. Breast cancer survivors with an expected survival of ≥ 5 years who are on long-term endocrine therapy are eligible.
 - o. Any other condition, impairment or social circumstance that, in the opinion of the Investigator, would render the patient not suitable to participate in the trial
 - p. Patient judged to be actively suicidal or a suicide risk by the Investigator
203. Known to have received reldesemtiv or tirasemtiv in any previous clinical trial

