9.4.1. General Considerations

Summary tables will present descriptive statistics such as number of patients, mean, median, standard deviation, minimum and maximum for continuous variables, and number of patients and the percentage for categorical variables, overall and by treatment in the planned analysis sets. For model-based analysis, least squares means, difference of least squares means between treatments, their standard errors and 95% confidence intervals (CI), and two-sided p-values for the relative statistical inferences will be presented. For survival analyses, time to event will be summarized by median, 95% CIs of median, and 1st and 3rd quartiles. Events and censored data points will be summarized by count and percentage. Hazard ratios between treatments and the corresponding 95% CIs and p-values will also be presented. Baseline is defined as the last available measurement taken before the first dose of randomized study drug received in the placebo control double-blind period unless otherwise specified. Analyses will be conducted by study period including the first 24-week double blind placebo-controlled period, the second 24-week active drug period, and the randomized delayed-start 48 weeks of treatment, and follow-up period.

Listings will include patient ID, demographics, treatment assigned and other relevant items, and sorted by treatment assignment, patient ID and date of assessment.

Unless specified otherwise, efficacy, safety and pharmacokinetics analyses will be performed on the full analysis set, safety analysis set and pharmacokinetics analysis set, respectively. Statistical analysis methods will be detailed in the SAP.

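### The mandatory combined liver stopping rule in Protocol 7.4 covers only patients with normal baseline enzymes, so it cannot fire for entrants whose ALT and AST are both already raised

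*Protocol*

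**What the plan says.** Protocol 7.4 has two sets of mandatory hepatic stopping criteria.

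- **Stand-alone criteria.** Stop if ALT or AST is above 8x ULN; if it is above 5x but below 8x ULN for two weeks or more, or without enhanced monitoring; or if it is above 3x ULN with "clinical signs or symptoms that are consistent with hepatitis (such as right upper quadrant pain/tenderness, fever, nausea, vomiting, jaundice"). All four rows apply to 'Any' baseline. TBL above 3x ULN also forces a stop.
- **Combined criteria.** Stop if all three hold: TBL above 2x ULN or INR above 1.5; "increased AST or ALT from the relevant baseline value as specified below"; and no other apparent cause. The table for the second condition has a single row, for baseline below ULN, with threshold above 3x ULN.

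On entry, exclusion 202g (Protocol 5.2) removes "ALT or AST $\geq 3 \times$ ULN at screening". Inclusion 110 (Protocol 5.1) accepts laboratory values within range, "or if outside the normal range, not deemed clinically significant by the Investigator". Bilirubin is held to a stricter limit: 202i excludes "Total bilirubin (TBL), direct or indirect bilirubin above the ULN".

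Section 7.4 does not define baseline. Protocol 9.4.1 does: "Baseline is defined as the last available measurement taken before the first dose of randomized study drug".

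**The concern.** The combined rule is meant to catch a transaminase rise accompanied by impaired liver function before either is extreme. As written, it does this only for patients who start with a normal enzyme. Patients who enter with both ALT and AST between ULN and 3x ULN are eligible, yet no threshold is given for them anywhere in the protocol.

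This is a patient-safety matter. Protocol 2.3.1 reports ALT or AST above 3x ULN in 24 patients (7.0%) on reldesemtiv against 1 (0.9%) on placebo in CY 5022, with dose dependence. All six patients with TBL above 2x ULN were on reldesemtiv. Section 2.3.1.1 names 7.4 as part of the hepatic mitigation strategy. Planned exposure here is 24 or 48 weeks, against 12 weeks in CY 5022.

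**Working it through.** **1. Who can enter.** 202g and inclusion 110 together admit ALT and AST from ULN to just under 3x ULN. The result is the same whether baseline means the screening value or the last pre-dose value.

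**2. Apply the combined rule.** All conditions must hold, and the enzyme condition exists only for baseline below ULN.

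| Baseline ALT / AST | Can the combined rule fire? |
|---|---|
| Both below ULN | Yes |
| One below ULN | Yes, through that enzyme. Through the raised one, only if the two are not judged separately, which the wording does not settle |
| Both at or above ULN | No, on any reading |

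Enumerating the rules over a grid of baselines and on-treatment values, with each enzyme judged on its own baseline, gives the same picture. Where the bilirubin/INR condition and an enzyme above 3x ULN are both met, the rule fires in 12,936 of 12,936 cells (both normal), 42,336 of 51,744 (one normal) and 0 of 51,744 (both raised). In 8,880 of the last group no mandatory rule of any kind applies. These are grid cells, not patient frequencies.

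**3. What remains uncovered.** After the stand-alone criteria, the gap needs all of the following:
- both enzymes at or above ULN before dosing;
- ALT or AST above 3x ULN but short of the stand-alone limits;
- TBL above 2x and up to 3x ULN;
- no hepatitis signs or symptoms, including no jaundice;
- no other cause.

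INR above 1.5 could replace the TBL condition, but only if INR happens to be measured. The scheduled tests do not include it: "ALT, AST, alkaline phosphatase (ALP) and total, direct, and indirect bilirubin will be obtained in accordance with the schedule of events". Section 7.4 asks for "bilirubin (total and direct), and obtaining an INR within 48 hours" among the assessments after permanent discontinuation.

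**4. Worked example.** Both enzymes 1.3x ULN at baseline, then ALT 4.5x ULN and TBL 2.5x ULN, asymptomatic, no other cause. ALT is not above 5x, TBL is not above 3x, and the combined rule has no row for this baseline, so there is no mandatory stop. From a baseline of 0.8x ULN the same readings require permanent discontinuation.

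**5. Likely number of cases (TBL limb only; Protocol 2.3.1 gives no INR data).**
- CY 5022 randomized 458 patients 1:1:1:1, so about 458/2 = 229 received 150 or 300 mg bid.
- TBL above 2x ULN at those doses: 6 − 5 = 1 patient. The text rules out concurrent ALT/AST above 5x ULN for that patient but is silent on 3x to 5x, so the combined pattern occurred in 0 or 1 of 229.
- Taking 1: 1/229 = 0.44%, exact (Clopper-Pearson) 95% CI 0.01% to 2.41%.
- Let f be the share entering with both enzymes raised. The documents do not give it, so it is assumed. Expected uncovered cases = 555 × rate × f.

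| f (assumed) | rate 0.44% | rate 2.41% |
|---|---|---|
| 1% | 0.02 | 0.13 |
| 5% | 0.12 | 0.67 |
| 10% | 0.24 | 1.34 |

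At the upper limit, f must reach 1/(555 × 0.0241) = 7.5% before one case is expected. If the single case was on 300 mg, the denominator is about 458/4 ≈ 115. The rate is then 1/115 = 0.87%, and f = 10% gives 555 × 0.0087 × 0.10 = 0.48.

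**6. Reporting.** SAP 9.5 states its liver category counts, including ALT and/or AST above 3x ULN with TBL above 2x ULN, for patients with normal baseline. A raised-baseline case would not appear in that table.

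**The case against.** The strongest reply is that the gap is small and well surrounded. The pattern needs several conditions at once, and Protocol 2.3.1 says transaminase rises in CY 5022 were overall not accompanied by raised bilirubin. Five of the six bilirubin cases were at 450 mg bid, which is not used here. The bilirubin and Gilbert's-type exclusions may lower the rate further; whether CY 5022 had them is not stated. An investigator may hold drug (a hepatic hold is itself permanent), adverse events of special interest are reported within 24 hours, and the DMC includes a hepatologist. The repeat-testing paragraph in 7.4 can be read as reaching patients still on drug. All of this stands and limits the size of the problem, but none of it is a mandatory stop.

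A table row could have been lost when the PDF was read. The text shows no sign of this: header, row and the following connective run on without a break. The sponsor can settle it by looking at the source.

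It can also be said that 'Any' weakens the reference to baseline, and that a Day 1 value is not capped by the screening limits, so the rule might fire without a rise. But the lead-in still requires an increase from baseline, so an unchanged value would not qualify. A multiple-of-baseline row would be a workable alternative.

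On the SAP point, raised-baseline cases remain visible in the laboratory and special-interest listings, and the shift, special-interest and time-to-elevation summaries are not stated as restricted to normal baseline. The omission is confined to the category counts and is minor.

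**Conclusion.** The concern holds. For patients whose ALT and AST are both at or above ULN before dosing, the mandatory combined rule cannot operate, and a defined set of readings that stops other patients is left to judgement for them. That conclusion follows from the text alone.

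The size is uncertain but probably small: below one expected case at the 0.44% rate for every f considered, and 1.34 at the upper limit with f = 10%. These figures assume equal Phase 2 arms, that the one lower-dose bilirubin case also had ALT or AST above 3x ULN, that the 12-week rate carries over to this trial, and that raised baseline enzymes do not alter risk. They are illustrative rather than a firm bound. Because the event is potentially serious and the correction simple, this should be fixed despite the low expected count.

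**What to change.** In the combined-rule table of Protocol 7.4, replace the below-ULN entry with 'Any', keeping the 3x ULN threshold and the lead-in wording. Entry bilirubin must be at or below ULN, so TBL above 2x ULN is a new change whatever the enzyme baseline. Screening ALT and AST must be below 3x ULN, so a value above 3x ULN always exceeds the screening value.

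In SAP 9.5, count the combined ALT/AST and bilirubin category in all patients, split by normal or raised baseline.

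The cost is one table cell in a protocol amendment, with IRB/IEC approval (Protocol 10.1.1) and communication to about 85 sites, plus one SAP sentence. The downside is a few more permanent discontinuations, some after a small enzyme rise (for example 2.9x to 3.1x ULN), but only when TBL exceeds 2x ULN or INR exceeds 1.5 and no other cause is apparent.

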7.5. Discontinuation from Study Procedures

Not applicable.

7.6. Patient Consent Withdrawal

Patients have the right to withdraw consent and no longer participate in the trial at any time and for any reason without prejudice to their future medical care by the physician or at the institution. Consent withdrawal means the patient no longer wishes to undergo any follow-up visits, study procedures, investigator contact, and non-patient contact follow-up (eg, medical records check).

- Discontinuing study drug should be distinguished from consent withdrawal for follow-up since the patient may agree to undergo study procedures or still be contacted even though they have stopped taking study drug.
- Consent withdrawal should be accompanied by documentation of the reason for withdrawal for patients willing to provide it. If the patient is unwilling to provide the reason, that should be recorded.

Patients who withdraw consent should be asked explicitly about the contribution of possible AEs to their decision to withdraw consent, and any AE information elicited should be documented.

Preferably, the patient should withdraw consent in writing and, if the patient or the patient's representative refuses or is physically unable, the site should document and sign the reason for the patient's failure to withdraw consent in writing; if the patient is unwilling to provide the reason, that too should be documented. The ICF for the trial should note that although a patient is free to leave the trial and stop taking study drug, the investigators hope the patient will remain for follow-up status evaluations.

For patients who have withdrawn consent for further follow-up, investigators and/or a third party retained by Cytokinetics may review public records as permitted by the ICF and applicable law to determine vital status of the patient at the end of the trial or before.

7.7. Lost to Follow Up

A patient will be considered lost to follow-up if he or she repeatedly fails to return for scheduled visits and is unable to be contacted by the study site.

The following actions must be taken if a patient fails to return to the clinic for a required study visit:

- The site must attempt to contact the patient or the patient's family and reschedule the missed visit as soon as possible and counsel the patient on the importance of maintaining the assigned visit schedule and ascertain whether the patient wishes to and/or should continue in the trial.
- Before a patient is deemed lost to follow up, the investigator or designee must make every effort to regain contact with the patient or the patient's family (where possible, 3 telephone calls and, if necessary, a certified letter to the patient's last known mailing address or local equivalent methods). These contact attempts should be documented in the patient's medical record.

- Should the patient continue to be unreachable, he/she will be considered to have discontinued from the trial and are lost to follow-up.

Closing of specific sites or discontinuation of the trial are handled as part of Appendix 1 (Section 10.1.8).

8. STUDY ASSESSMENTS AND PROCEDURES

There will be up to eight clinic visits and nine remote visits (with most requiring an accompanying phone or video call), with windows to aid in scheduling as shown in [Table 3](#). If a patient visit must be scheduled outside the visit window, the Medical Monitor should be contacted. If a patient is scheduled for an in-clinic visit outside the visit window, the ALSFRS-R should be obtained by phone or video call during the visit window when possible, while the other visit related procedures will be obtained outside of the visit window when the patient is seen in clinic. Day 1 anchors all subsequent study visits.

Table 3: CY 5031 Visit Windows

Visit	Visit Window	Home FVC Window*
Screening: clinic visit/lab		
Start of Dosing (Day 1): clinic visit/lab	Up to 21 days following Screening	1-3 days prior to Day 1
End of Week 2: remote – lab only	14 days \pm 2 days	
End of Week 4: clinic visit/lab	28 days \pm 4 days	\pm 2 days of clinic visit
End of Week 8: remote visit/lab	56 days \pm 4 days	
End of Week 12: clinic visit/lab	84 days \pm 4 days	\pm 2 days of clinic visit
End of Week 16: remote visit/lab	112 days \pm 4 days	
End of Week 20: remote visit/lab	140 days \pm 4 days	
End of Week 24 (last dose of double-blind dosing): clinic visit/lab	168 days \pm 4 days	1-3 days prior to clinic visit
End of Week 26: remote – lab only	182 days \pm 2 days	
End of Week 28: remote visit/lab	196 days \pm 4 days	
End of Week 32: remote visit/lab	224 days \pm 4 days	
End of Week 36: clinic visit/lab	252 days \pm 4 days	\pm 2 days of clinic visit
End of Week 40: remote visit/lab	280 days \pm 4 days	
End of Week 44: remote visit/lab	308 days \pm 4 days	
End of Week 48 (last dose of active drug dosing): clinic visit/lab	336 days \pm 4 days	1-3 days prior to clinic visit
Follow-Up (4 weeks after last dose of study drug): clinic visit/lab	364 days \pm 4 days	1-3 days prior to clinic visit

*With the exceptions noted, home FVC is performed on the same day as other procedures are done for the remote visit

Study procedures and their timing are summarized in the SoA ([Section 1.3](#)). Protocol waivers or exceptions are not allowed for inclusion/exclusion criteria.

Immediate safety concerns should be discussed with the Medical Monitor immediately upon occurrence or awareness to determine if the patient should continue or discontinue study drug.

Adherence to the trial design requirements, including those specified in the SoA ([Section 1.3](#)), is essential and required for trial conduct.

All screening evaluations must be completed and reviewed to confirm that potential patients meet all eligibility criteria. The investigator will maintain a screening log to record details of all patients screened and to confirm eligibility or record reasons for screening failure, as applicable.

Repeat or unscheduled samples may be taken for safety reasons or for technical issues with the samples.

If scheduled in-clinic visits are not possible, remote visits will be made and documented to review trial assessments, safety, adverse events, provide safety laboratory samples, and concomitant medications as detailed in the Study Manual (see [Section 4.1](#), Overall Study Design for additional details on converting in-clinic visits to remote visits).

